5.6 Follow up procedures

In the event of non-progression of cancer following the 12-month prostate biopsy, treatment with study medication will continue for the remaining six months of the trial, pending transfer to the main trial if the option is available.

Alternatively, if progression **is** seen at biopsy, as described in section 1.1, patients may exit the study. Tissue will be sought from patients undergoing radical prostatectomy providing it can be acquired before the participant attends their PROVENT End of Study appointment. This will be stored in the Orchid Research Tissue Bank.

5.7 Laboratory Assessments

In addition to the routine blood samples taken as standard practice in an Active Surveillance programme, a range of tests specific to the PROVENT study will also be collected. These will include six monthly serum Vitamin D3, androgen and calcium levels. Samples will also be taken at baseline and 18 months for translational research. These samples will be stored for future analysis to identify molecular and genetic markers of aggressive prostate cancer, as per the Laboratory Manual. Results of routine blood tests, including three monthly PSA, will be evaluated during the study.

Infection with *Helicobacter Pylori* (*H. Pylori*) will be assessed using a standard stool test at baseline only and tested locally in the laboratories at participating centres.

Urine samples will be collected at baseline and 12 months for exploratory research (see Section 2.2), and at baseline, 12 and 18 months for translational research as per the Laboratory Manual. Testing will take place in the Molecular Epidemiology Laboratory, Centre for Cancer Prevention, Queen Mary University of London.

Residual urine will be frozen locally at each site until shipped and finally stored within an ultra-low temperature freezer (-60 to -90°C), at the Molecular Epidemiology Laboratory, Queen Mary University of London, for future analysis to identify molecular and genetic markers of aggressive prostate cancer. They may also be made available to the scientific community outside of QMUL, for ethically approved research. Where this occurs, the samples will always remain pseudo-anonymised, i.e. identified by a unique identifier.

Paraffin embedded tissue will be collected from diagnostic biopsy samples taken prior to joining the study, and from samples collected at biopsy or surgery during/after the study, and stored by Queen Mary University of London until shipped for Cell Cycle Progression (CCP (ii)) score analysis by Myriad Laboratories, Salt Lake City, USA.

A minimum 10% sample of all prostate biopsy tissue received will undergo a central pathology review by the collaborating study pathologist at Centre for Molecular Oncology, Barts Cancer Institute, Queen Mary University of London to ensure consistency of reporting. Anonymised copies of all pathology report forms will be obtained for central review.

All prostate tissue samples will be sent to the Barts CTU who will arrange onward transfer to the appropriate laboratories. Tissue samples will be stored for future research in the Orchid Research Tissue Bank (ORTB), Barts Cancer Institute, Queen Mary University of London, as stated in the consent form, pending further ethical applications.

5.8 Radiology Assessments

Patients will undergo Magnetic Resonance Imaging (MRI) prior to entry and at 12 months as part of their routine treatment on Active Surveillance.

Progression of prostate cancer will be defined as the development of a lesion on multi-parametric imaging where no MRI lesion was identified on the screening MRI, or alternatively, an MRI scan that demonstrates that a lesion identified on screening MRI has increased in volume over the study period by greater than 33%.

Patients will undergo multi-parametric MRI imaging of the prostate. The scan will be performed & reported using each site's routine practice and locally defined parameters. The details of the procedure & the results will be recorded on a 'MRI Procedure & Results' eCRF. In addition, a pseudo-anonymised copy of the report will be uploaded to the PROVENT application.

5.9 End of Study Definition

The end of trial is defined as Last Patient Last Visit (LPLV), including at least 30 days for Pharmacovigilance reporting.

5.10 Procedures for Unblinding

A 24-hour unblinding service is not proposed for the PROVENT study, as it is felt that this is not required given the two particular medications being trialled.

Patients admitted as an emergency with bleeding or haemorrhage would be treated in the same way irrespective of any medication they might have taken, as the primary concern is to stop the bleeding. Salicylate levels would be taken to establish the presence of aspirin which would negate the need for unblinding.

In the event of an overdose of study medication (aspirin/ placebo and/or Vitamin D3/placebo) the patient should be referred immediately to an emergency care facility. In the majority of cases, treatment for suspected aspirin or Vitamin D3 overdose is the treatment of symptoms arising from the overdose.

If aspirin is taken in overdose, it is easily and quickly detected by measuring the patient's plasma salicylate level (salicylate is the active metabolite of aspirin). Plasma salicylate levels are routinely performed in all patients presenting to the emergency services with suspected aspirin overdose. The plasma salicylate level is readily available at very short notice in all district general hospitals throughout England and Wales. As such, any PROVENT trial patient presenting with an acute overdose of study medication would have their blood drawn for a plasma salicylate level which would identify immediately whether or not aspirin had been taken. While awaiting the test result, patients would be managed as if they had taken an overdose of aspirin. As for any patient presenting to the emergency services with a suspected overdose of aspirin, they would receive immediate assessment followed, in most cases, by gastric decontamination with activated charcoal - a medication that has no deleterious effects. Subsequent treatment would be governed by plasma salicylate levels in a similar manner to any patient with aspirin overdose.

In the case of Vitamin D3 overdose, no immediate effect will occur and, as such, a 24-hour unblinding service is not required. The potential complication is hypercalcaemia, however, chronic overdose of Vitamin D3 would be identified by serum calcium testing which is a requirement within the PROVENT study, at which point unblinding would be performed. If a patient presented to the emergency services with a suspected overdose of Vitamin D, be that an acute or chronic overdose, a serum calcium test would quickly identify that this was the case, allowing standard emergency care to be initiated, and rehydration considered in order to reduce the level of calcium in the blood.

Unblinding for any purpose other than a medical emergency will not generally be allowed, but individual cases should be discussed with the Chief Investigator if it is believed to be necessary for the medical care of the participant.

If an investigator considers it necessary to unblind a patient, requests for unblinding should be sent to the trial coordinating office using the Codebreak Request form. The CI or delegated individual e.g. the trial coordinator will consider the request and, if appropriate, the designated persons will unblind the patient according to the procedure described in the study unblinding document. All efforts should be made to limit unblinding of subjects in order to protect the integrity of the study.

Should a patient request that their treatment is unblinded, the subject must be withdrawn from the study and the details documented in the medical notes and End of Study CRF.

In the event of a treatment code being unblinded, the reason for this decision and the details of those involved in the decision should be documented in the participant's medical notes and, in the event of a Serious Adverse Event, on the SAE form. Unblinding details will be confidential and only those personnel that must be informed for medical management of the patient will be informed. Wherever possible, the patient himself should remain blinded. Members of the trial co-ordinating team should also remain blinded.

Aspirin overdose can cause hyperthermia, tachypnoea, respiratory alkalosis, metabolic acidosis, hypokalaemia, hypoglycaemia, hallucinations, confusion, seizures, cerebral oedema and coma, therefore if these conditions present they should be managed in a standard fashion in an emergency care unit.

Vitamin D3 overdose can cause nausea, vomiting, diarrhoea, constipation, loss of appetite, headache, tiredness, muscle and joint pain/weakness, thirst, polyuria and dehydration, and hypercalcaemia

5.11 Subject Withdrawal

Patients may withdraw from the trial at any time at their own request, or they may be withdrawn at any time at the discretion of the investigator if it is considered to be in the best interest of the patient. Patients can withdraw without giving a reason, but if a reason is given this should be documented on the relevant eCRF and medical notes.

(See section 3.4 for withdrawal criteria)

5.12 Data Collection and Follow Up for Withdrawn Subjects

Data collected up to the time of withdrawal of consent will be included in the study analyses, as stated in the consent form, unless participants specifically withdraw permission to do so in writing. With the exception of such patients, withdrawn subjects will remain under three monthly follow-up in clinic for the duration of the trial, as the main analyses will be by intention to treat.

6.0 Laboratories

6.1 Laboratories & Testing

Biochemistry Laboratories at participating centres

Routine blood testing for PSA will be carried out in local hospital laboratories as per standard procedure. Serum calcium and androgen levels will also be tested at these laboratories.

Clinical Biochemistry Laboratory, Royal London Hospital

This nominated hospital laboratory will batch test the serum vitamin D samples. The results of these tests will not be released to the research team, but only in an anonymised fashion to the Data Monitoring Committee.

Histopathology Laboratories at participating centres

Prostate biopsy samples will be examined at local accredited hospital laboratories, as per usual practice. Guidelines for standardised examination will be provided by [name], Professor of Genito-urinary pathology, St Bartholomew's Hospital

Molecular Epidemiology Laboratory, Centre for Cancer Prevention

This research laboratory, under the direction of [name], will carry out exploratory research tests on urine samples collected at baseline and 12months. This laboratory will also store frozen blood and urine samples collected at baseline and 18 months for future exploratory & translational research to identify molecular and genetic markers of aggressive prostate cancer,

Myriad RBM

CCP (ii) score analysis. Formalin-fixed paraffin embedded tissue samples from baseline and 12 months sent in prepared batches to the Myriad laboratories. In addition, the laboratories will receive 15ml baseline, 12 month and End of Study, residual urine samples, for translational research, from each participant. No additional samples are being requested from the patients to facilitate the provision of this.

6.2 Sample collection/labelling/logging

Samples for local testing will be taken as per normal local practice.

Samples taken in addition to normal practice will be de-identified and labelled with a unique identifier and logged in the Case Report Form as detailed in the PROVENT Laboratory Manual.

6.3 Sample Receipt/Chain of Custody/Accountability

Handling of the samples in the laboratories will be as per the PROVENT Laboratory SOPs. Upon arrival at the laboratory staff will ensure that the physical integrity of these samples has not been compromised in transit and that all samples are accounted as per the labeling. The samples should be logged on receipt in an accountability log as documented in the laboratory SOP.

6.4 Sample Analysis Procedures

Standard tests carried out routinely in the local laboratories include blood testing for PSA, serum androgen levels and corrected calcium. In addition, a standard faecal Helicobacter pylori test will be carried out locally.

The non- standard tests are for research purposes only and are not diagnostic. These include serum Vitamin D3 levels, urine samples for exploratory and translational research, prostate tissue samples for CCP (ii) Score analysis and translational research, and blood samples for translational research.

6.5 Sample Storage Procedures

Samples that will not be tested immediately will be stored as detailed in the PROVENT Laboratory SOP.

6.6 Data Recording/Reporting

For locally performed testing, data will be recorded in the patient record as per standard practice. The local PI or delegate will transcribe relevant results into the eCRF which will hold the data.

All other research testing will be recorded by individual laboratories and transferred to the PROVENT Co-ordinator as detailed within individual agreements.

See also Section 9.0 for data confidentiality

7.0 Pharmacovigilance

7.1 General Definitions

7.1.1 Adverse Event (AE)

(See Appendix 2 for Safety Reporting Flowchart)

An AE is any untoward medical occurrence in a subject to whom a medicinal product has been administered, including occurrences which are not necessarily caused by or related to that product. An AE can therefore be any unfavourable and unintended sign (including an abnormal laboratory finding), symptom or disease temporarily associated with the use of an Investigational Medicinal Product (IMP), whether or not considered related to the IMP.

7.1.2 Adverse Reaction (AR)

An AR is any untoward and unintended response in a subject to an Investigational Medicinal Product (IMP), which is related to any dose administered to that subject. All adverse events judged by either the reporting investigator or the Sponsor as having a reasonable causal relationship to a medicinal product qualify as adverse reactions. The expression reasonable causal relationship means to convey in general that there is evidence or argument to suggest a causal relationship.

7.1.3 Serious Adverse Event (SAE) or Serious Adverse Reaction (SAR)

An SAE fulfils at least one of the following criteria:

- Is fatal results in death
- Is life-threatening

- Requires inpatient hospitalisation or prolongation of existing hospitalisation
- Results in persistent or significant disability/incapacity
- Is a congenital anomaly/birth defect

Since there is no risk arising from the transfer of any PROVENT IMP products via seminal fluid, it has been deemed unnecessary to collect & record pregnancies where the father is a PROVENT study participant.

Serious Adverse Reaction (SAR)

An SAR is an adverse reaction that is classed as serious and which **is consistent with** the information about the medicinal product as set out in the Summary of Product Characteristics (SmPC) for Aspirin or Vitamin D3.

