2.2 Secondary Objectives and Endpoints

Objectives	Endpoints	Assessment Method
To report response to treatment as determined by serial multiparametric magnetic resonance imaging (MRI) of the prostate.	The development of a lesion on multi-parametric imaging where no MRI lesion was identified on screening MRI, an MRI scan that demonstrates that a lesion identified on the screening MRI has increased or decreased in volume by greater than 33%, or an upgrading of MRI stage of disease to ≥T3. 50% increase in serum PSA at 12 months from baseline	Results collected on Case Report Forms (CRFs) after MRI scanning
To report biochemical disease progression	Histological disease progression will be defined as an increase in Gleason	Routine 3-monthly blood samples
To report histological disease progression	scores from: Gleason 3+3 to Gleason score 7 or higher Gleason 3+4 (score 7) to 4+3 (score 7) or Gleason 4+3 to a higher score Or a 50% increase in maximum cancer core length (MCCL)	Routine 12-month biopsy
To assess consistency in local reporting and establish the necessity for central review of the pathology reports, in the main		Central review of at least 10% of all prostate biopsy tissue
trial. To report toxicity and/or allergy to both aspirin and Vitamin D3	Aspirin toxicity: Haemorrhagic stroke, anaphylaxis following administration, gastrointestinal bleeding requiring intervention (both medical and surgical) Vitamin D3 toxicity: Hypercalcaemia, Anaphylaxis	Adverse events recorded on the CRF 3-monthly up to month 15 th , and then for a further 4mths.
To evaluate an association between androgens and disease progression		Blood sample for serum Vitamin D3 and corrected calcium levels 6 monthly

To evaluate markers of disease progression

Cell Cycle Progression (CCP(ii)) scores

Cell Cycle Progression (CCP(ii)) scores

Urine sample and testing at Molecular Epidemiology Laboratory, QMUL

See Section 5.7 for details of laboratory assessments

Prostate biopsy tissue testing by Myriad Genetics

MRI imaging will be reported according to local practice. Lesion volumes will be measured by planimetry on all sequences. Diffusion and/or dynamic contrast enhancement sequences will be included in this assessment [43]. Scans will be reviewed locally by a specialist radiologist, and the baseline and subsequent scan directly and concurrently compared.

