Repeat biopsies may occur from week 48 to week 56 depending on clinic waiting times; therefore study medication may be taken for up to four weeks more, or less, than 12 months in the weeks leading up to the routine biopsy.

Patients will undergo biopsy with prophylactic antibiotic administration as per normal procedures. This may be either a TRUS biopsy or a template biopsy and performed under local anaesthesia or general

anaesthesia using a 12 Hz ultrasound probe. The procedure will comprise a standard systematic biopsy together with targeted biopsies taken from any MRI detected abnormalities.

Biopsy cores should be sent to local laboratories separately from each region of the prostate, with no more than two cores per pot, and labelled according to the region of the prostate sampled. In patients with MRI detected prostate lesions, at least one targeted biopsy core should be directed to each lesion and placed in a separately labelled pot. Tissue taken will be processed locally as per the PROVENT Laboratory Manual.

If clinically necessary, repeat biopsy can be brought forward, or not performed, at the discretion of the Investigator. Alternatively, a patient may decide to leave the trial and undergo radical prostate cancer therapy during the 18-month study period; however the case should be presented at a multidisciplinary team meeting before an alternative management strategy is commenced. Patients who undergo radical treatment will stop trial medication at this point and not be followed up. Patients remaining on Active Surveillance but not undergoing a repeat biopsy will remain in the study for analysis as PSA dynamics over the study period will still be available.

Abnormal laboratory test results

A laboratory abnormality in one of the study specific tests, such as serum corrected calcium or H Pylori, may require the subject to undergo treatment. A value flagged, for example, as 'clinically significant' must be entered on the Adverse Event CRF. In addition, the test may need to be repeated at the Investigator's discretion. The Investigator may use his/her own judgment as to whether the abnormal finding is sufficient reason to immediately withdraw the patient from the study.

Any laboratory value that meets the definition of Serious Adverse Event must be reported as an SAE (refer to 7.1.3). In addition, the patient should be reassessed for continuation in the study and any indicated and appropriate therapies should be initiated.

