7.2.4 Severity

The Principal Investigator must assess the severity of the event according to the following terms and assessments. The intensity of an event should not be confused with the term "serious" which is a regulatory definition based on patient/event outcome criteria.

Mild: Some discomfort noted but without disruption of daily life **Moderate:** Discomfort enough to affect/reduce normal activity

Severe: Complete inability to perform daily activities and lead a normal life

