7.3 Notification and reporting of Adverse Events or Reactions

If the AE is not defined as serious, the participant is followed up by the research team. The AE is documented in the participants' medical notes (where appropriate) and the CRF. (See Appendix 2 for Flowchart for Safety Reporting)

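### The definitions of seriousness (7.1.3) and severity (7.2.4) have no medical-importance or laboratory criterion, so they cannot rank symptom-free hypercalcaemia, a named Vitamin D3 toxicity on which IMP is stopped

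*Protocol*

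**What the plan says.** **Seriousness.** Section 7.1.3 opens with "An SAE fulfils at least one of the following criteria" and gives five: death, "Is life-threatening", "Requires inpatient hospitalisation or prolongation of existing hospitalisation", disability or incapacity, and congenital anomaly. Section 7.2.1 ties the investigator's judgement of seriousness to the definitions in 7.1.

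**Severity.** In section 7.2.4 the lowest grade is "Some discomfort noted but without disruption of daily life". The two higher grades are worded as reduced normal activity and complete inability to carry on daily life. The same section warns that intensity and seriousness are different things.

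**Laboratory findings.** Section 7.1.1 allows an abnormal laboratory finding to be an AE. Section 5.4 puts clinically significant values on the AE CRF and adds: "Any laboratory value that meets the definition of Serious Adverse Event must be reported as an SAE (refer to 7.1.3").

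**Named toxicities.** Section 2.2 lists "Vitamin D3 toxicity: Hypercalcaemia, Anaphylaxis". Under aspirin it lists, among others, gastrointestinal bleeding requiring medical or surgical intervention. Section 4.11 discontinues IMP when hypercalcaemia is confirmed by blood sample, with no condition about symptoms. Section 3.4 lists a calcium above the upper limit of normal or 2.65 mmol/l as a possible reason for withdrawal.

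**Reporting.** Section 7.3: "If the AE is not defined as serious, the participant is followed up by the research team", with the event entered in the notes and CRF. Section 7.4.1 requires SAEs to reach the CTU within 24 hours and has the Chief Investigator review every SAE.

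**The concern.** The protocol treats a laboratory-confirmed raised calcium as important enough to be a toxicity endpoint and to end treatment. Its two classification scales have nothing to measure that finding with. The seriousness list contains only outcomes, and the severity scale contains only symptoms and function. A slightly raised and a markedly raised calcium, both found on a scheduled test in a man who feels well, receive the same label.

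This matters for two reasons. Seriousness decides which events go to the CTU within 24 hours and receive the Chief Investigator's individual review. Also, sections 2.3 and 8.1 make the case for the main trial depend partly on adverse effects being minimal in every arm. For the harm that the Vitamin D3 arms are specifically monitored for, the severity label says nothing about the size of the abnormality and so cannot inform that judgement.

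**Working it through.** No arithmetic decides this point. The check follows each kind of event through the definitions in turn.

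| Event | Seriousness (7.1.3) | Severity (7.2.4) | Route |
|---|---|---|---|
| Raised calcium, no symptoms, no admission | Non-serious unless life-threatening | At most mild; arguably not gradable, since mild requires some discomfort | AE CRF |
| Raised calcium with symptoms, no admission | Non-serious unless life-threatening or disabling | Mild to severe, by symptoms | AE CRF |
| Raised calcium leading to admission | Serious | By symptoms | SAE, 24 hours |
| Gastrointestinal bleeding treated medically, no admission | Non-serious unless life-threatening or disabling | By symptoms | AE CRF |

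The reasoning behind the table is as follows.

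1. *Is there another way into the seriousness list?* Section 7.2.1 refers the assessor back to 7.1, and section 5.4 refers laboratory values back to 7.1.3. Neither adds a judgement-based item, so the five outcomes are the only way in.
2. *Do symptoms make an event serious?* No. Section 7.2.4 separates the two scales. Symptoms can raise severity, but the second row stays non-serious without admission, threat to life or disability.
3. *Can the measured value change the grade?* No. Section 7.2.4 contains no laboratory bands, although 7.1.1 admits laboratory findings as AEs.
4. *What does non-serious status change?* Section 7.3 sets no time limit for a non-serious event. The 24-hour rule and the case-by-case review in 7.4.1 cover SAEs only. Sections 7.2.2 and 7.2.3 require causality and expectedness assessments only for serious events.
5. *What else does the protocol attach to the same finding?* It is an endpoint (2.2), stops IMP once confirmed (4.11) and may lead to withdrawal (3.4).

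*Who is exposed.* Section 3.1 puts 17 men in each of six arms, and section 5.3 lists the arms.

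- Vitamin D3: 3 arms × 17 = 51 men.
- Aspirin, either dose: 4 arms × 17 = 68 men.

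The protocol gives no rate of hypercalcaemia. If it were 2% to 6% over the study (an assumption for scale only), the number would be 0.02 × 51 = 1.0 to 0.06 × 51 = 3.1, so about one to three men. The argument does not depend on this rate.

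**The case against.** The strongest reply is that nothing is lost. A clinically significant value must go on the AE CRF (5.4), and section 3.4 has the CRFs collect gastrointestinal bleeding and hypercalcaemia specifically. The eCRF is fully accessible to the coordinating centre (9.3). The Chief Investigator's annual risk-benefit analysis covers all events (7.6). The DMC reviews toxicity data at least six-monthly (8.3, 10.0) and sees unblinded comparisons by arm. Seriousness, severity and action on treatment are also separate concepts, so stopping IMP for a non-serious event is not in itself a contradiction. All of this stands, and it rules out several stronger readings that a reader might infer:

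- *That these events stay with the site or drop out of the safety picture.* They do not. They miss only the expedited route and individual SAE review.
- *That the by-arm comparison is distorted.* Nothing in 2.2, 8.3 or 10.0 filters toxicity by seriousness or severity. A mild label does not remove an event from the count; it only fails to say how large the abnormality was.
- *That hypercalcaemia in general triggers unblinding.* Section 5.10 mentions "serum calcium testing which is a requirement within the PROVENT study, at which point unblinding would be performed", but the sentence concerns chronic Vitamin D3 overdose identified by that testing.
- *That SUSARs are being missed.* A SUSAR must also be unexpected against the product information, which is not shown, and the protocol itself describes hypercalcaemia and gastrointestinal bleeding as known effects.
- *That every confirmed hypercalcaemia ought to be an SAE whatever its outcome.* That would be a debatable policy choice, not the correction of an error.

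The reply does not supply a criterion for medically important events or a way to grade a laboratory finding. The content of the Appendix 2 flowchart and the separate SAE reporting plan listed in 9.2 are not available. Either might escalate further events, but the definitions that investigators are told to apply are those in 7.1.

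**Conclusion.** The point holds as a gap in classification. The seriousness list has no medical-importance item, and the severity scale cannot grade a laboratory-only event. Hypercalcaemia is one of two named Vitamin D3 toxicities, the other being anaphylaxis. It is non-serious unless fatal, life-threatening, disabling or a cause of admission, and without symptoms it is at most mild whatever the value. Gastrointestinal bleeding managed medically without admission is non-serious on the same terms, unless life-threatening or disabling.

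The practical effect is modest: no 24-hour report, no case-by-case SAE review, and a severity label that carries no information about the calcium level. The men concerned are few and their events are still recorded and reviewed. The conclusion rests on the printed definitions and assumes that the safety documents not shown do not widen them. It is a cheap improvement worth making, not a failure of safety oversight.

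**What to change.** Reconcile 7.1.3 and 7.2.4 with 2.2, 4.11 and 5.4:

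1. In 7.1.3, add that an event the investigator judges medically important is serious even if none of the five listed outcomes applies. Section 5.4 then works as written, because laboratory values sent to 7.1.3 meet a criterion that can apply to them.
2. In 7.2.4, state that AEs detected by laboratory test are graded by the measured value, in bands agreed in advance with the DMC. Keep the present wording for symptomatic events.
3. Give the DMC a table of the highest on-treatment corrected calcium for each man, by arm, so that the judgement in 2.3 and 8.1 rests on values as well as labels.

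The cost is wording in two sections, a few additional SAE forms and one table. Calcium is already measured six-monthly, so no new tests are needed. No clinical threshold or stopping rule is proposed.
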